Blinding will be involved in this study. The primary investigator, study participants, and team members involved in serum/urine end point analyses will be blinded to treatment arm. The investigational pharmacy is responsible for study group assignment and is not blinded. The study team member involved in the fecal bacterial genome analysis will not be blinded, as knowledge of treatment arm will be necessary for the accurate assessment of changes in fecal microbiome composition among study participants.

3. State the maximum number of subjects to be enrolled in each group. Include power calculations to explain what can be studied with the proposed sample size and specify the statistical tests that will be used to test **each** hypothesis. If the research project needs to be pilot tested, state how many subjects will be enrolled in the pilot test and how the procedures for the pilot test will differ from those used in the research protocol.

There will be a total of 30 subjects enrolled; 15 participants will receive Rifaxmin and 15 will receive placebo.

D. Subject Criteria (See Vulnerable Populations appendix, if applicable): Include age range, gender, disease, and stage of treatment. Justify excluding subjects based on race or

gender (including child-bearing potential for women), age (children), or non-English speakers.

- 1. Inclusion criteria: State the criteria for inclusion in the study in a specific and detailed manner.
 - Patients 18 years of age or older
 - Stage IV-V chronic kidney disease (eGFR ≤ 39 ml/min/1.73m²)
- 2. Exclusion criteria: State the criteria for excluding potential subjects from the study in a specific and detailed manner.
 - Patients with normal renal function or those with less advanced kidney disease
 - Inability or unwillingness to provide consent
 - Patients undergoing hemodialysis or peritoneal dialysis therapy or those who have undergone organ transplant
 - Patients who may be pregnant
 - Hemodynamically unstable patients
 - Patients with liver failure, pancreatic insufficiency, or inflammatory bowel disease
 - Patients with ongoing or recent infection and those with history of C-diff infection
 - Patients with abnormal bowel structure secondary to surgical or anatomic variations
 - Patients on certain medications including immunosuppressants, antidiarrheal agents, and current or recent (within the last 2 months) use of antibiotics

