Blood, urine and stool samples will be labeled with study information and by the subjects' unique study ID. They will be analyzed in the lab of [name] and the lab of [name] at the University of Pittsburgh Medical Center. Additional serum and urine samples will be stored in a -80°C freezer in [name] lab for those patients consenting for sample storage.

5. Timeline: Consider attaching a study flow chart illustrating subject visits and tests or procedures to be performed at each visit **and/or** include a chart or graph format that reflects the project activities and anticipated time frame of completion.

Day 0 (baseline visit): Consented participants will have an initial appointment dedicated to the collection of baseline samples and study medication will be dispensed at this visit. Complete review of the patient's history and physical examination will be recorded. All study participants will continue receive standard of care treatment for their chronic kidney disease. Study participants will be provided with a 10-day course of Rifaximin. A medical history will be obtained, including current medications, comorbid conditions, lifestyle indicators (such as tobacco and alcohol use), review of recent laboratory studies (such as BMP, CBC, and lipids); this information will be recorded and stored on all study participants. Serum, urine and fecal samples will be collected at this

visit. On Day 1, study participants will begin Rifaximin 550mg PO BID or placebo for a total of ten days duration.

Day 11 (post-therapy follow-up visit): Study participants will provide stool samples within 24 hours of their last dose of Rifaximin or placebo. Serum and urine samples will be drawn at this study visit. Vital signs will be checked and a brief interview will be conducted to assess for any potential adverse reactions to the study medication. Follow up visits can be arranged at the patient's request if needed.

Day 25 (steady state follow-up visit): Study participants will provide stool samples. Serum and urine samples will be drawn at this study visit. Vital signs will be checked and a brief interview will be conducted to assess any recent health changes.

- **F. Risk/benefit assessment:** As appropriate, address the following parameters as each relates to the individual subject in the study. Be sure to include consideration of study assignment (Arm A, Arm B, placebo, active substance, etc):

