- 1. Physical risk: Rifaximin has known potential side effects. Since this medication has primarily been studied in patients with advanced liver disease, it is unclear which of these side effects are unique to this population of patients. The most common side effects reported in patients with liver disease included peripheral edema, ascites, nausea, dizziness, fatigue, headache, muscle spasms, pruritus, abdominal pain, and rash. Most common side effects in patients without liver disease are believed to be gastrointestinal in nature; mainly including nausea, abdominal pain/bloating, and diarrhea. Serious reactions have been reported by the manufacturer with this therapy, including superinfection with clostridium difficile, hypersensitivity reaction, angioedema, anaphylaxis, and exfoliative dermatitis. The risks associated with venipuncture in order to obtain blood samples carries a small risk of excessive bleeding, vasovagal syncope, hematoma/infection at the site of vein puncture, and potentially multiple punctures in order to locate veins.
- 2. Psychological risk: No anticipated risk.
- 3. Social risk: No anticipated risk.
- 4. Economic risk: Low anticipated risk. The patient will have no cost associated with the study. In the instance of an adverse event, normal medical treatment should be sought and insurance billed as is standard.
- 5. Potential benefit of participating in the study:
 - a. To the individual subject and/or parent if any: Individuals are not expected to benefit directly from participation in this study.
 - b. To the population from which the subject is drawn: This study may provide critical insight into understanding the altered metabolism of TMAO in CKD and provide preliminary evidence to support the development of future large-scale studies.
 - c. To science, society, and humanity in general: This may lead to development of interventions which could decrease the burden of cardiovascular disease in patients with chronic kidney disease, ultimately reducing health care costs and outcomes for patients with these conditions.
- **G. Location where study will be performed:** Indicate where all portions of the study will take place and where the research subject's records will be kept.

This study will be conducted at the University of Kansas Hospital with patients being recruited from the outpatient nephrology clinics. Records will be kept on secure spreadsheets that can only be accessed by the study team.

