- 1. Please note that any study proposal with more than minimal risk must include a data and safety monitoring plan. Elements of the plan include:
 - a. Persons/groups who will review the data (study team; independent safety monitor, data monitoring committee or formal DSMB)
 The study team
 - b. Data/events that will be reviewed
 Adverse reactions, early discontinuation, tolerance and side effects.
 - c. Frequency of review

 After ten days of therapy and PRN.
 - d. Types of analyses to be performed Patient interview
 - e. Safety-related triggers that would cause the PI to stop or alter the study Multiple adverse reactions may lead the team to reconsider the dose or the chosen agent.
- 2. Describe how adverse events and unanticipated problems will be ascertained and handled. Explain exactly which type of problems will be considered serious and reported to the IRB. The reporting timeframe should also be detailed.

Participants will be given contact information for KU nephrology on-call numbers. There have been rare serious adverse medication reactions with Rifaximin, including intestinal

superinfection, C-diff associated diarrhea, angioedema, or exfoliative dermatitis. In these instances a patient will be instructed to seek emergency medical attention.

3. Explain exactly what will happen if a patient experiences an adverse event or other problem (for example, will discontinue study participation).

Patients will be asked to report any adverse reaction. They will be given the contact information for the nephrology nursing line who can contact a member of the study team. This is a short study lasting 25 days and patients will have 3 total study visits, on day 0, day 11, and day 25.

III. Subject Participation

A. Recruitment:

1. Describe locations from which the subjects will be recruited and what arrangements have been made with other institutions (if applicable).

The initial contact will occur at KU nephrology clinic. There will not be outside institutions involved.

2. Describe by whom and how the recruitment is conducted.

A subject's primary treatment team will be the initial contact to gauge interest in learning about the study. From there a member of the study team will discuss the study in further detail.

3. Attach a copy of advertisements and/or flyers and state where they will be placed.

There will not be advertisements or flyers.

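### The safety review schedule does not name the day 25 visit, the day 11 and day 25 interviews ask different questions, and the two lists of serious reactions disagree

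*Combined protocol and SAP*

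**What the plan says.** Four places in the combined protocol bear on this point.

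- **Data and safety monitoring plan, item 1.c (frequency of review):** "After ten days of therapy and PRN". Item 1.a gives the reviewer as the study team, and item 1.d gives the patient interview as the only form of analysis.
- **Section II.E.5 (Timeline), dosing and visits:** "On Day 1, study participants will begin Rifaximin 550mg PO BID or placebo for a total of ten days duration". At day 11, "a brief interview will be conducted to assess for any potential adverse reactions to the study medication". At day 25, "Vital signs will be checked and a brief interview will be conducted to assess any recent health changes".
- **Section II.F.1 (Physical risk), serious reactions reported by the manufacturer:** "superinfection with clostridium difficile, hypersensitivity reaction, angioedema, anaphylaxis, and exfoliative dermatitis".
- **Data and safety monitoring plan, item 2:** a list of rare serious reactions, introduced as examples. It begins with intestinal superinfection and goes on to the instruction to patients: "superinfection, C-diff associated diarrhea, angioedema, or exfoliative dermatitis. In these instances a patient will be instructed to seek emergency medical attention".

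Item 3 of the monitoring plan adds that patients will be asked to report any adverse reaction, gives them a nursing line that can reach the study team, and restates the three visits on days 0, 11 and 25.

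**The concern.** The protocol follows patients to day 25, but the only review time it names is tied to the end of dosing. Since the patient interview is the only stated analysis, its wording is in effect the safety instrument, and that wording changes between the two post-dosing visits. Two things follow.

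- **Elicitation.** A patient who develops diarrhea after day 11 and does not call is next seen on day 25. The scheduled question there is about general health and does not mention the study drug. Whether the answer is recorded as a possible adverse reaction depends on how the patient and the interviewer take the question.
- **Review.** The plan does not say that the study team will look at what was learned on day 25. The trigger in item 1.e for altering the study is multiple adverse reactions, so it depends on late events reaching the team as such. Section IV.E.2 states that there is no third-party monitoring to catch them.

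The list in item 2 raises a different matter. It is attached to an instruction to patients, and it is also the only text under a prompt that asks which problems will be treated as serious and reported. If it differs from the list in the risk section, staff have two accounts of which reactions are serious.

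**Working it through.** The plan gives no numerical figure for this point to reproduce. The check is day arithmetic and a comparison of texts.

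**1. Last dosing day.** First dose on day 1 for ten days (section II.E.5): 1 + 10 − 1 = day 10.

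**2. Time covered after dosing.**
- Last dosing day to day 11 visit: 11 − 10 = 1 day.
- Last dosing day to day 25 visit: 25 − 10 = 15 days.
- Between the two visits: 25 − 11 = 14 days.

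So 14 of the 15 days of follow-up after dosing come after the visit that matches the only review time named in item 1.c.

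**3. The two visits compared.**

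| | Day 11 | Day 25 |
|---|---|---|
| Vital signs | yes | yes |
| Interview | yes | yes |
| Subject of interview | adverse reactions to study medication | recent health changes |
| Matched by item 1.c | yes, as the end-of-therapy review | not named; as-needed review only |

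The visits differ in the question asked and in whether a review is scheduled. Both include contact with the patient.

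**4. The two lists compared.**

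| Reaction | Section II.F.1 | Monitoring plan, item 2 |
|---|---|---|
| C. difficile | listed | listed |
| Angioedema | listed | listed |
| Exfoliative dermatitis | listed | listed |
| Hypersensitivity reaction | listed | absent |
| Anaphylaxis | listed | absent |
| Intestinal superinfection | only as C. difficile | listed separately |

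Three reactions are shared. Two of the five in section II.F.1 are missing from item 2, and item 2 has one entry that the risk section does not list separately.

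**5. Effect on event counts.** The documents give no event rates for either period and no detection probability for either form of question. The number of late events affected cannot be calculated, and none is offered here.

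**The case against.** The strongest reply is that safety contact plainly continues after day 11. Day 25 has vital signs and an interview, a question about any change in health is broader than one about drug reactions, and new diarrhea or a C. difficile diagnosis would be a proper answer to it. Patients are asked to report any adverse reaction, without a time limit, and have numbers to call. As-needed review is part of item 1.c itself. All of this stands. It rules out any statement that late events would be missed; the documents support only that they may be captured less consistently.

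Three further inferences may tempt a reader, and the documents do not support them.

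- **That allergic events go uncollected because two terms are missing from item 2.** That list concerns what patients are told to do and is introduced as examples. What is reviewed is set by item 1.b, which covers adverse reactions in general. What participants are actually told also cannot be judged here, because the consent pages are not in the reviewed text.
- **That follow-up is too short by the protocol's own standard, because it excludes patients with** "current or recent (within the last 2 months) use of antibiotics". That is an eligibility criterion with no stated rationale. In a study of gut flora it may serve only to protect the baseline samples. It sets no safety window, so 15 days of follow-up does not contradict it.
- **That a stated objective of the trial is compromised.** Tolerability is not among the aims in section I.A or the objectives in section II.A. Both arms get the same questions at each visit, so no bias between arms is shown.

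What the reply leaves untouched is that item 1.c omits day 25, that the interviews are worded differently with no reason given, and that the lists do not match.

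**Conclusion.** The point holds as a matter of consistency in safety ascertainment. For 14 of the 15 days after the last dosing day, the plan relies on a general health question, spontaneous reports and as-needed review, whereas the period up to day 11 has a targeted question and a scheduled review. Separately, two of the five reactions that the risk section calls serious are absent from the list tied to the emergency-care instruction. The primary comparison of serum TMAO is unaffected.

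This rests on two readings. The first is that item 1.c refers to the day 11 visit, the first visit after the course ends; if the study team already meant it to cover day 25 as well, the text should say so. The second is that the interviews will be conducted as worded. The matter is still more than a missing detail: section II.F.1 says that it is unclear which known side effects are specific to patients with liver disease, so what this pilot records about tolerance in kidney disease has some value, and the correction is very cheap.

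**What to change.** 1. In item 1.c of the monitoring plan, name the day 25 visit as a scheduled review alongside the end-of-therapy review, and keep the as-needed provision.
2. In section II.E.5, use the same set of adverse-reaction questions at days 11 and 25. The day 25 question on recent health changes can stay as an addition.
3. Reconcile the serious reactions in section II.F.1 with those in item 2 of the monitoring plan, so that the two agree or the difference is explained. Which reactions belong there, and what patients are told to do about each, is for the sponsor and investigators to settle.

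The cost is a wording change in three places and a few more interview questions for up to 30 participants at a visit already scheduled. No new visit, sample or participant is needed.

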University of Kansas Medical Center RESEARCH PROTOCOL INVOLVING HUMAN SUBJECTS TEMPLATE WITH GUIDANCE

Version date: 8/11/2015

Principal Investigator: [name].

Study Title: Impact of Rifaximin Therapy on Intestinal Byproducts in Chronic Kidney Disease

Co- Investigator(s): [name], D.O.

[name], M.B., BChir [name]. [name] [name] [name]

(NOTE: not all sections of this template will apply to all projects. "N/A" is an acceptable response.)

I. Purpose, Background and Rationale

A. Aim and Hypotheses

1. Begin with a brief introduction to describe the origin and importance of the study.

Trimethylamine-N-oxide (TMAO) is a circulating organic compound produced by the metabolism of dietary L-carnitine and choline. TMAO was recently identified to directly induce atherosclerosis in rodents and is strongly associated with the incidence of cardiovascular events in humans. The proposed investigation is a prospective pilot study to assess the impact of alterations in the intestinal flora by short-term antibiotic suppression (with Rifaximin) and to measure its effect on serum TMAO levels in patients with advanced-stage (stage IV-V) chronic kidney disease.

2. Clearly state the aim(s) and hypothesis(es), listing them by number if there is more than one.

Hypothesis: Treatment of CKD patients with Rifaximin will suppress the bacterial flora that are responsible for the generation of trimethylamine, a TMAO precursor, and subsequently reduce serum TMAO concentrations.

Primary Aim:

 The primary outcome of interest will be the change in serum TMAO concentrations (post-therapy minus pre-therapy TMAO) following Rifaximin administration for 10 days.

Secondary Aims:

- 1. To measure the change in urine TMAO
- 2. To measure the change in serum endotoxin, IL-6, IL-8, TNF-alpha levels
- 3. To measure the alteration of bowel microbiota
- 4. To assess the above changes in steady state, 2 weeks after completion of therapy

B. Background and Significance

1. Study Significance: what the proposed research is intended to accomplish and the importance of the results

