in rodents and was found to be strongly associated with the incidence of cardiovascular events in humans (2-5). In normal physiologic conditions, circulating TMAO is rapidly removed from circulation primarily by excretion into the urine (7). We previously postulated that TMAO levels would be substantially elevated in patients with CKD, and to test this hypothesis we performed a cross-sectional analysis of serum TMAO concentrations in a cohort of patients with varying levels of CKD and normal healthy controls. In this study, we observed serum TMAO concentrations become markedly elevated in the advanced stages of CKD, with end-stage renal disease (ESRD) patients exhibiting mean levels 30-fold higher than healthy controls.

If TMAO contributes to atherosclerosis formation in CKD patients, therapeutic interventions to reduce TMAO production may represent a method to reduce cardiovascular morbidity and mortality in this population. Prior studies suggest that short-term suppression of gut flora with antibiotics dramatically decreased TMAO levels in patients with normal kidney function (5); however, this approach has not yet been tested in patients with CKD that exhibit much higher serum levels of TMAO.

Rifaximin is a novel antibiotic that is currently approved for treatment of hepatic encephalopathy in patients with end-stage liver disease. Rifaximin demonstrates little systemic absorption, with 97% of the parent drug being excreted unchanged in the feces (9). Its primary use is to target pathogenic intestinal bacteria in various disease states , including cirrhosis and traveler's diarrhea. In this study we seek to evaluate whether Rifaximin will decrease levels of TMAO in patients with advanced kidney disease and to study the effects of Rifaximin on the intestinal microbiome of patients with CKD.

Explain how the performance of this proposed project will advance our knowledge in this field, and/or improve our understanding of the disease or physiological condition being studied.

This study will determine if elevated levels of TMAO in CKD are at least partially dependent on the presence of certain intestinal flora and if serum TMAO levels are modifiable by therapy with Rifaximin.

3. Explain how this study might improve the diagnosis or treatment of the disease being studied (if applicable), or advance knowledge in the field.

This will provide preliminary evidence to support the intestinal flora as a target for reducing TMAO levels in CKD patients.

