II. Research Plan and Design

A. Study Objectives: List the broad research goal and specific aims of the project in a clear, concise manner using lay language. List primary and secondary; include statement of purpose. (NOTE: the Department of Biostatistics is available to assist with study design, sample size calculation, and statistical analysis matters. Contact [name] or see Consulting and Collaboration at Department of Biostatistics

Primary objectives: To determine if administration of Rifaximin for the period of 10 days reduces serum TMAO levels.

Secondary Objectives: To determine if Rifaximin additionally alters urine TMAO, serum endotoxin,IL-6, IL-8, TNF-alpha, and the composition of the intestinal flora and the composition of the intestinal flora as compared to placebo.

B. Study Type and Design: Indicate type of study (e.g. cross-sectional vs. longitudinal; multicenter, controlled, cross-over, randomized, chart review, case cohort, non-interventional, etc) and describe how the study is to be conducted to accomplish specific aims of the project.

This is a prospective, randomized, placebo-controlled, double-blinded interventional pilot study.

C. Sample size, statistical methods, and power calculation

1. Describe the analytic and statistical methods to be used, including the method of randomization and randomization ratio (1:1; 3:1; etc) if randomization is used.

We seek to enroll a total of 30 patients for this investigation, 15 participants will receive Rifaximin and 15 control patients will receive placebo with a 1:1 randomization ratio. No prior data are available on the impact of rifaximin on serum TMAO levels in CKD patients; therefore, our sample size determination is based on a conservative estimate of the predicted change in TMAO and the expected response variability between study participants. Based on an expected true mean change in serum TMAO concentrations in matched pairs of -30% with a standard deviation of -30% change, we will need to study 13 subjects to be able to reject the null hypothesis that this response difference is zero with 90% power and type I error probability of 0.05. We plan to enroll 15 subjects in our intervention groupin case the observed variability in this response is greater than our initial prediction.

2. If blinding (masking) is involved, describe the procedures, indicate who has the code to the blind, and the circumstances and procedures for breaking the code.

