D. Procedures to protect subject confidentiality: Identify any part of the study that may place subject confidentiality at risk. Describe study procedures to protect subject confidentiality.

The researchers will only use and share information that is needed for the study. Identifying information collected may include such information as name, address, phone, date of birth, or other identifiers. Participants health information will be reviewed at KUMC by [name], members of the research team, The University of Kansas Hospital Medical Record Department, the KUMC Research Institute and officials at KUMC who oversee research, including members of the KUMC Human Subjects Committee and other committees and offices that review and monitor research studies. Data will be de-identified prior to analysis and prior to outside involvement in the study.

E. Quality Assurance / Monitoring

1. Describe steps to be taken to assure that the data collected are accurate, consistent, complete and reliable. (source data verification, audits or self – assessment)

Self-assessment.

2. Describe whether there are plans to have ongoing third party monitoring.

There is no plan for third party monitoring.

V. Data Analysis and Reporting

A. Statistical and Data Analysis: A description of the statistical methods to be employed in data analysis, including timing of any planned interim analysis

The study will be considered complete when the necessary power is obtained. A paired, two-sided Student's t-test will be used to compare differences in pre-antibiotic and post-antibiotic TMAO levels.

B. Outcome: Describe what results are expected, the criteria for success or failure and the end point of the study.

We expect that our intervention will lead to significant short-term reductions in serum TMAO levels.

C. Study results to participants: List any study results to be given to subjects and indicate how, when and why they will be given.

Study findings may be discussed at the conclusion of the study by participant request.

D. Publication Plan: Describe plans for publication of research results.

Results may be published in abstract form or as part of a peer-reviewed original research manuscript.

- **VI. Bibliography / References / Literature Cited** (choose the applicable title and list citations according to APA or other accepted style in your discipline)

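### The only planned test is a before-and-after paired t-test; nothing in the plan compares serum TMAO change on rifaximin with placebo

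*Combined protocol and SAP*

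**What the plan says.** Section II.B sets the design: "This is a prospective, randomized, placebo-controlled, double-blinded interventional pilot study". Section II.C.1 gives the allocation: "15 participants will receive Rifaximin and 15 control patients will receive placebo with a 1:1 randomization ratio".

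The primary endpoint and objective do not mention placebo. Section I.A has "The primary outcome of interest will be the change in serum TMAO concentrations (post-therapy minus pre-therapy TMAO) following Rifaximin administration for 10 days", and section II.A has "To determine if administration of Rifaximin for the period of 10 days reduces serum TMAO levels".

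Section V.A, the whole of the statistical analysis text, names one test: "A paired, two-sided Student's t-test will be used to compare differences in pre-antibiotic and post-antibiotic TMAO levels". It does not say which patients enter that test. The template item at II.C.3 asks for the test of each hypothesis, and the reply gives only the group sizes.

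The sample size in II.C.1 rests on an "expected true mean change in serum TMAO concentrations in matched pairs of -30" percent, with an SD of 30% (printed with a minus sign). It arrives at 13 subjects for 90% power and raises this to 15 for the intervention group.

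A comparison with placebo is mentioned only in the secondary objectives (II.A), which end with "the composition of the intestinal flora as compared to placebo". No test is attached to it.

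**The concern.** The rationale (I.C) says the study will determine "if serum TMAO levels are modifiable by therapy with Rifaximin". A Day 0 to Day 11 change in treated patients cannot show that by itself. It is the drug effect plus whatever else moves TMAO over those days: diet, the effect of being in a trial, assay drift. The protocol itself describes TMAO as a product of dietary carnitine and choline, and its procedures do not standardise diet. The placebo arm is there to remove these shared influences, and the named test makes no use of it for that purpose.

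Followed as written, the analysis could declare rifaximin effective when placebo patients improved equally. If the test is run only in treated patients, which is the likelier reading, the 15 placebo patients contribute nothing to the primary result. Leaving the between-arm comparison unwritten also means that it would have to be chosen after the data are seen.

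**Working it through.** **Inputs.** From II.C.1: mean change −30%, SD of change 30%, power 90%, type I error 0.05, 15 per arm. From V.A: paired t-test, two-sided. Assumed, because the documents give no figure: the size of any non-drug change, the SD in the placebo arm (taken as 30) and the placebo mean change (taken as 0 unless stated).

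**1. Reproduce the stated 13.** The power of a paired t-test comes from the noncentral t distribution with n − 1 degrees of freedom and noncentrality d√n, where d = 30/30 = 1.

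- n = 12: noncentrality √12 = 3.46, power 88.3%
- n = 13: noncentrality √13 = 3.61, power 91.1%
- n = 15: noncentrality √15 = 3.87, power 94.9%

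The smallest n reaching 90% is 13, as stated. The figure is arithmetically right, but it answers a single-arm before-and-after question and uses no placebo data.

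**2. Paired test in 15 rifaximin patients when the drug does nothing.** Suppose TMAO falls by δ points in both arms for non-drug reasons. The noncentrality is (δ/30)√15.

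| Shared fall δ (assumed) | Noncentrality | Paired test significant | Between-arm test significant |
|---|---|---|---|
| 0 | 0 | 5.0% | 5% |
| 5 | 0.65 | 9.2% | 5% |
| 10 | 1.29 | 22.5% | 5% |
| 15 | 1.94 | 43.8% | 5% |
| 20 | 2.58 | 67.1% | 5% |

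The between-arm test is unaffected because the shared fall cancels in the difference.

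**3. Other readings of V.A.**

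- *All 30 patients pooled.* The noncentrality becomes (δ/30)√30, and false significance is 14.3%, 42.3% and 75.4% at δ = 5, 10 and 15.
- *Each arm tested separately.* The chance of a significant result on rifaximin and a non-significant one on placebo, with no drug effect, is p(1 − p). This is 0.092 × 0.908 = 8.4% at δ = 5, 0.225 × 0.775 = 17.5% at δ = 10, and 0.438 × 0.562 = 24.6% at δ = 15.

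None of these readings tests the difference between arms.

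**4. Power once the arms are compared.** A two-sample t-test of change with n per arm has 2n − 2 degrees of freedom and noncentrality d√(n/2). With n = 15 and d = 1 this is √7.5 = 2.74, and power is 75.3% (78.2% by the normal approximation).

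- 90% power needs 23 per arm (46 in total); 80% needs 17 per arm (34 in total).
- At 15 per arm the detectable difference is 31.8 points for 80% power and 36.8 points for 90%.
- Power at 15 per arm by SD: 88.7% (SD 25), 75.3% (30), 62.0% (35), 50.9% (40).
- If placebo falls by 5 or 10 points and the rifaximin change stays at −30, power is 59.6% or 42.2% (SD 30).

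Baseline adjustment could improve on these figures, but the documents give no pre/post correlation, so the gain cannot be quantified.

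**The case against.** The best defence is that the design is sound and the comparison remains available. Both arms give the same samples on Days 0, 11 and 25, and those analysing serum and urine are blinded. The secondary objectives show that a comparison with placebo was intended, and V.A does not say that placebo patients are left out. On this view the contrast is merely unwritten, in a pilot study.

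Part of this stands. The fault lies in the planned analysis and not in the trial, and restriction of the test to treated patients is an inference, though the reference to antibiotic and the intervention-group sample size both support it. But step 3 shows that no reading of V.A compares the arms. The pilot label does not help either, because the protocol states a powered hypothesis test and expects a significant reduction.

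It is also fair that the false-positive rates rest on assumed shifts. No section documents any non-drug change, and with none the paired test keeps its 5%. The SD is on the percent-change scale, while V.A refers to levels, so the rates apply if percent change is what is analysed. The rates for separate tests in each arm concern a procedure that the protocol does not propose; they only show that it would be no remedy. These points limit the size of the problem and leave the omission in place.

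**Conclusion.** The concern holds. No analysis in the plan tests rifaximin against placebo for the primary endpoint, or for any other endpoint, in a randomised placebo-controlled trial. Under the analysis as written, a TMAO change cannot be attributed to rifaximin. With SD 30 and 15 treated patients, false significance would be 9.2% to 43.8% for illustrative shared falls of 5 to 15 points, against 5% for a between-arm test. This affects the primary conclusion and should be corrected before unblinding.

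**What to change.** Replace the test in V.A with wording such as: *Primary analysis: ANCOVA of log serum TMAO at Day 11 on randomised arm, adjusted for log Day 0 TMAO, in all randomised participants with a Day 11 value, analysed in their assigned arm, two-sided 0.05. The result is the rifaximin/placebo ratio with its 95% confidence interval.* The log scale suits an effect that the protocol expresses as a percentage. A two-sample test of the change from Day 0 would also cure the defect and stays closer to the stated post-minus-pre endpoint, but one of the two must be named in advance.

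Also:

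- Add the comparison with placebo to the primary aim and objective.
- Keep within-arm paired tests as descriptive only.
- Use the same between-arm model for urine TMAO, endotoxin, IL-6, IL-8 and TNF-alpha at Day 11, and for these and serum TMAO at Day 25. Label them secondary and say how multiplicity is handled.
- Name a between-arm method for microbiome composition, which this model does not cover.

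The cost is text: no new samples or visits, and no added enrolment if 30 patients are kept. The 90% power claim must then be replaced by about 75% for an unadjusted between-arm test with 15 per arm (SD 30 in both arms, no placebo change). Keeping 90% would take 23 per arm on the same assumptions. V.A also ties completion of the study to reaching the necessary power, so that sentence should give way to a fixed sample size.
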